1 BACKGROUND AND PROJECT RATIONALE

Echocardiography is an established specialty with dedicated tools, which require a lot of know-how both in manipulation and interpretation [1, 2]. Most cardiac patients who are prescribed a Computed Tomography scan (CT scan), or a Magnetic Resonance Imaging exam will undergo transthoracic echocardiography in the first place. The Prospective Cardiac Ultrasound Imaging Study aims at collecting cardiac ultrasound data from patients diagnosed with ventricular tachycardia. The research will analyse the ultrasound image data quality and establish if it is appropriate to develop a new medical device supporting automated cardiac ultrasound image interpretation during non-invasive cardiac procedures, i.e. ventricular tachycardia stereotactic radioablation. Such device would allow for a new way of monitoring patients during hospital procedures.

This early research protocol will collect data from volunteer patients. The data will not be used for diagnostic nor treatment purposes and the protocol's procedure duration is limited, hence the research is of very limited risk for the participants. The research has the potential to enable the creation of a medical device that will benefit patients with ventricular tachycardia and other cardiac pathologies in the future.

2 PROJECT OBJECTIVES AND DESIGN

2.1 Primary objective

The primary objective of the research is to evaluate the ultrasound image quality for arrhythmia patients, to investigate potential echogenicity and artefact issues, which may arise from age, body composition, mechanical valves, leads from implanted devices, etc. in order to have a representative sample of the variety of ventricular tachycardia patients.

2.2 Primary and additional endpoints

Objectives

The primary research objective is the proportion of subjects who have a positive evaluation in image interpretation metric and positive visual inspection of the ultrasound images.

Secondary objective; Additionally, for patients for whom a full field of view CT scan is available, the theoretical impact of probe positioning during a CT scan is analysed for hypothetical treatment planning.

Endpoints

Primary

The objective will be quantitatively assessed by scoring each patient as follows:

- A) Cardiac motion analysis performance:
 - o Score 1 if analysis of the ultrasound images with the EBAMed software gives a cardiac phase error (within R-R interval) < 0.1
 - o Score 0 otherwise
- B) Respiratory motion analysis performance:
 - o Score 1 if analysis of the ultrasound images with the EBAMed software gives a motion amplitude lower than 30 mm and if the number of breathing cycles matches the one observed from the motion of the chest.
 - o Score 0 otherwise

- C) Image quality performance:
 - o Score 1 if visual inspection by a member of San Matteo team can identify in the ultrasound images at least one of these structures: left ventricular wall, interventricular septum, or heart valve.
 - o Score 0 otherwise
- D) Image quality performance :
 - o Score 0 if visual inspection by a member of San Matteo team identifies that the heart becomes invisible for part of the time due to tissue motion linked to respiration.
 - o Score 1 otherwise

For each patient, scoring will be done for each imaging view (parasternal and apical). If the score is 2 (at least 1 point in A or B and 1 point in C or D) or higher for at least one of the imaging views, the outcome will be considered as positive. The final result will be the proportion (in %) of patients with a positive outcome defined as the number of patients with a positive evaluation divided by the total number of patients x 100.

Secondary

The objective will be quantitatively assessed by scoring each patient (only those with a CT available):

- with Score 1: if a successful radio-ablation treatment plan respecting dose constraints can be created using a clinical treatment planning software (see details below) and,
- with Score 0: if it is not possible to create such a treatment plan .

The final result will be the proportion of patients (in %) with a 1 Score: number of patients with score 1 divided by the number of patients with Score 0 or 1 x 100.

The treatment plan is performed with the Raystation clinical treatment planning software by a Medical Physicist from the EBAMed team. An electrophysiologist from the San Matteo team will draw on the CT the contours of a realistic ventricular tachycardia ablation treatment target and the contours of relevant organs-at-risk (including e.g. adjacent cardiac substructures, oesophagus, stomach and trachea). An additional virtual structure will be contoured on the CT, representing the position of the ultrasound probe (based on the best probe view as assessed by scoring for the primary endpoint). A successful treatment plan will need to accomplish all of the following:

- radiation beams do not go through the ultrasound probe
- treatment target receives at least 25 Gy (typical treatment dose)
- organs at risk receive a dose below the threshold given in Table 1

Table 1: OARs and their relevant metrics (some taken from literature¹, others from consultations with early implementers).

OAR	Relevant Metric	Limit
Whole heart – PTV	*D(50%Volume)	< 5 Gy
Non-involved myocardium = Left ventricular wall + right ventricular wall – PTV	V(20Gy)	Low as possible
Left Atrium	*Dmax	< 4.4 Gy
Mitral valve	Dmax	< 14 Gy
Aortic valve	Dmax	< 14 Gy
Left-anterior-descending coronary artery	*Dmax	< 14 Gy
Aorta	*Dmax	< 20 Gy
Superior Vena Cava	*D(50%Volume)	< 0.6 Gy
Whole Lungs	*V(total) – V(7Gy), D(5%Volume)	> 1500 cc
Spinal Canal	*Dmax V(6Gy)	< 7 Gy < 0.1cc
Oesophagus	*Dmax V(9Gy)	< 14.5 Gy < 1cc
Skin	*Dmax V(10Gy)	< 14.4 Gy < 10 cc
Trachea	*Dmax V(10Gy)	< 15 Gy < 1 cc
ICD (electronics)	*Dmax	< 0.5 Gy

Data that may influence the results will be collected such as patient’s demographics and cardiovascular history.

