2.3 Project design

This is a single center, one arm, feasibility study. The patients will undergo one Cardiac motion monitoring procedure to collect ultrasound imaging data via the Demonstrator 2 developed by EBAMed SA, Switzerland and there is no follow-up planned.

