3 STUDY POPULATION AND PROCEDURES

3.1 Study population, inclusion and exclusion criteria

The study will enrol up to 24 adult patients diagnosed with ventricular tachycardia.

Patients with cardiac or non-cardiac implants in the thorax area are of interest for the research.

Patients of all relevant ages and gender should be represented in the final study population.

Inclusion criteria:

1. Patient with history of ventricular tachycardia
2. Over 18 years old
3. Ability and willingness to provide written informed consent

Exclusion criteria:

1. Patient in arrhythmic storm

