4 STATISTICS AND METHODOLOGY

4.1. Statistical analysis plan

Sample Size. This is a feasibility study at early research stage. We plan to enroll 24 patients. We aim at a feasibility of 90% for the primary endpoint (success in 22/24 pts). With 24 patients and an expected proportion of 90%, the lower limit of the 95% confidence interval (95%CI) will be 73% (precision 17%); with an expected proportion of 95% (success in 23/24 pts), the lower limit of the 95%CI would be 79% (precision 11%).

Data Analysis. The number and proportion of success for the primary and secondary endpoint will be reported with their 95%CI. The proportion of success and 95%CI will also be reported by patients characteristics (for instance, but not limited to: age \leq / $>$ 65; BMI overweight/normo-underweight), gender, VT etiology)

Descriptive statistics (mean and standard deviation/median and quartiles or counts and percent) will be reported for the population description.

-

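### The secondary objective is the probe's impact on planning, but every plan includes the probe, so the endpoint measures feasibility and only bounds the impact

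*Protocol*

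**What the plan says.** Section 2.2 of the protocol states the secondary objective for patients with a full field of view CT: "the theoretical impact of probe positioning during a CT scan is analysed for hypothetical treatment planning". It is assessed by one binary score per patient. Score 1 means that a plan meeting the constraints can be made. The alternative is worded "with Score 0: if it is not possible to create such a treatment plan", with no cause attached. The result is the percentage of scored patients with Score 1.

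The same section describes how the plan is built: "An additional virtual structure will be contoured on the CT, representing the position of the ultrasound probe", placed at the best view from the primary scoring. Success requires three things jointly:

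- "radiation beams do not go through the ultrasound probe";
- the target reaches its required dose;
- "organs at risk receive a dose below the threshold given in Table 1".

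Section 2.3 describes the design: "This is a single center, one arm, feasibility study". Section 3.1 sets the ceiling on numbers: "The study will enrol up to 24 adult patients diagnosed with ventricular tachycardia". The number expected to have a CT is not given. For the analysis, section 4.1 says: "The number and proportion of success for the primary and secondary endpoint will be reported with their 95%CI". It adds the same summary by patient characteristics. The protocol describes no plan without the probe and no plan at a second probe position.

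**The concern.** An impact is a difference between two conditions. Here the difference would be between what can be planned without the probe and what can be planned with it. The protocol observes only the second.

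A Score 1 is informative: the probe did not prevent a plan in that patient. A Score 0 is ambiguous. The probe may have blocked the beams, or the target and anatomy may have ruled out an acceptable plan regardless. Reporting by patient characteristics does not help, because every subgroup is also planned with the probe in place.

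What is at stake is the interpretation of failures. Section 1 says the study is meant to inform development of a device for use during radioablation. If some patients score 0, the report could not say whether the probe or the anatomy was responsible. Changes in plan quality among patients who still score 1 are not measured at all.

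**Working it through.** **Inputs from the protocol.** At most 24 patients (3.1, 4.1); one score per patient with a CT (2.2); three joint success criteria, one of them about the probe (2.2); one proportion with a 95% CI (4.1). The number with a CT and the failure rate are not stated, so the counts below are assumptions.

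**Interval method.** The protocol gives no figure for the secondary endpoint. For the primary endpoint, section 4.1 states a lower limit of 73% for 22/24 and 79% for 23/24. Exact Clopper-Pearson limits are 73.0% to 99.0% and 78.9% to 99.9%, so both stated lower limits reproduce. The same method is used here.

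**Bound on the loss due to the probe.**

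1. Let n be the patients with a CT, s those with Score 1, and z = n − s those with Score 0. Let k be the Score 0 patients who could be planned without the probe, with 0 ≤ k ≤ z.
2. A plan that succeeds with the probe also meets the other two criteria without it. Every Score 1 patient is therefore plannable without the probe.
3. Plannable with the probe = s/n. Plannable without it = (s + k)/n. Loss due to the probe = (s + k)/n − s/n = k/n.
4. The planned data do not determine k, so the loss can be anything from 0 to z/n. The lower end applies if all Score 0 patients would fail anyway, and the upper end if all could be planned without the probe.

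**Numbers put in.**

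| Assumed result | Reported | Exact 95% CI | k | Plannable without probe | Loss (points) |
|---|---|---|---|---|---|
| 18/24 | 75% | 53.3% to 90.2% | 0 | 18/24 = 75% | 0 |
| 18/24 | 75% | 53.3% to 90.2% | 3 | 21/24 = 87.5% | 3/24 = 12.5 |
| 18/24 | 75% | 53.3% to 90.2% | 6 | 24/24 = 100% | 6/24 = 25 |
| 9/12 | 75% | 42.8% to 94.5% | 0 to 3 | 75% to 100% | 0 to 25 |
| 23/24 | 95.8% | 78.9% to 99.9% | 0 to 1 | 95.8% to 100% | 0 to 4.2 |

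The reported proportion and interval are the same for every k.

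**Limiting case.** If all patients score 1, z = 0 and the loss in the sample is 0. The exact 95% upper limit on the Score 0 share is then still 14.2% for n = 24, 26.5% for n = 12 and 36.9% for n = 8.

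**The case against.** The strongest reply is that the protocol defines its own objective. It says how the objective will be assessed, and probe avoidance is an explicit success criterion. On that reading, the impact simply means whether an acceptable plan remains possible with the probe in place, which is the useful question for a one-arm feasibility study. It stands that the proportion is valid for that question. But the stated objective is then worded more broadly than the endpoint supports, and the wording invites attribution of failures to the probe.

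The objective could also be read as concerning where the probe sits, rather than probe versus no probe. That reading leaves the same gap, because only the best view is planned and no second position is compared.

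The planner will know which criterion failed, and recording that could be left to the SAP or the case report form. This would help description, but the criteria trade off against one another: a plan that misses an organ limit may do so because the beams were routed around the probe. The failed criterion does not show what was possible without the probe, and no later analysis can recover a plan that nobody made.

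Two objections stand in part. The 25-point figure follows entirely from an assumed 25% failure rate, and nothing in the protocol makes that likelier than results where the issue nearly vanishes. A second planning attempt made only for failures can also move a score only upward. Such a rescoring is nevertheless consistent with Score 1, which asks whether a plan can be created.

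**Conclusion.** The concern holds as a minor point. The endpoint answers whether a plan can be made with the probe in place; it does not estimate the probe's impact. The yes/no loss due to the probe is bounded by 0 and the Score 0 share, and nothing in the planned data narrows that range. The bound rests on one assumption: removing the probe cannot make a plannable patient unplannable.

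The size depends on how many patients fail, which the protocol does not predict. It ranges from nothing in the sample if all succeed to the full Score 0 share. The consequences are limited, because this is a secondary endpoint in the CT subset, the plans are hypothetical and no decision rule depends on it. The primary endpoint is unaffected.

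**What to change.** Amend section 2.2 in one of two ways.

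**Option 1: add the missing comparison.** For each patient scored 0, make one plan on the same CT, with the same target and organ contours. Remove the probe structure and the probe-avoidance criterion, and leave the other criteria unchanged. Set the planning effort in advance and keep it the same for both plans; the protocol does not currently define it. If the probe-free plan happens to avoid the probe, it is also a valid plan with the probe, and the patient is rescored 1. Report the proportion plannable with the probe, the proportion plannable without it (counting all Score 1 patients as plannable), and the difference as the yes/no loss due to the probe. State that the second attempt may overstate this loss.

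The cost is one extra in-silico plan per Score 0 patient (six in the 18/24 illustration), with the same staff and software and no patient procedure. Plan quality among Score 1 patients remains unmeasured.

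**Option 2: narrow the claim.** Restate the secondary objective and the intended conclusion as feasibility of planning with the probe in place, and do not attribute failures to the probe. The cost is one reworded sentence and no extra work, but the probe's impact is then not studied.

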3.1.1 Demographics and cardiovascular history

The patient will be asked to confirm his/her demographics and cardiovascular history.

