3.1.2 Cardiac Motion monitoring

The following procedure steps will take place:

- The study system is installed in the room before patient arrival
- The patient needs to *fully* undress the upper body before lying on the bed
- The 3 ECG electrodes are placed
- Ultrasound gel is applied on the ultrasound probe

A – Apical view

- The ultrasound probe is positioned for apical viewing and fixed with the probe holder and the probe holder strap around patient's chest. Probe position is recorded on case report form. The relative position of the probe is automatically recorded via is optical localization system.
- The cardiac motion monitoring can start. During data acquisition, the image quality of the ultrasound images is visually monitored. The following data sequences are acquired successively:
 1. Patient in free breathing, 5 minutes
 2. Next 5 minutes, the patient starts holding breath for 10 seconds, repeated every minute (total: 5 breath holds in 5 minutes)
- Ultrasound probe, probe holder and strap are removed

B – Parasternal view

- The ultrasound probe is positioned for parasternal viewing and fixed with the probe holder – when available and stable - or held manually.
- The following data sequences are acquired successively:
 1. Patient in free breathing, minimum 1 minute, goal: 5 minutes with fixed probe position
 2. Next 5 minutes, the patient starts holding breath for 10 seconds, repeated every minute (total: 5 breath holds in 5 minutes), with fixed probe position. Note: this step is required when probe holder is in use, and optional when probe is manually held.
- The patient is offered tissues to remove ultrasound gel before dressing up
- The patient is asked whether he/she experienced any discomfort during the procedure

The procedure is performed by a trained investigator. The Cardiac Motion monitoring procedure will last for up to one (1) hour.

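### The subjective image scores C and D may be read by any site team member, with no masking, so expectation can bias the primary proportion and, above all, its breakdown by patient characteristics

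*Protocol*

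**What the plan says.** Protocol section 2.2 builds the primary endpoint from two software items (A, cardiac phase; B, respiratory motion) and two visual items (C and D). C reads "Score 1 if visual inspection by a member of San Matteo team can identify in the ultrasound images at least one of these structures", the structures being the left ventricular wall, the septum or a valve. D reads "Score 0 if visual inspection by a member of San Matteo team identifies that the heart becomes invisible for part of the time" because of respiration, and is 1 otherwise. Each view, apical and parasternal, is scored, and the patient is positive if at least one view meets the rule: "If the score is 2 (at least 1 point in A or B and 1 point in C or D) or higher".

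On who is present at acquisition, section 3.1.2 says "The procedure is performed by a trained investigator" and "During data acquisition, the image quality of the ultrasound images is visually monitored". Section 3.1.1 says "The patient will be asked to confirm his/her demographics and cardiovascular history", and the schedule in section 3.3 puts this under the procedure.

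On purpose, section 2.1 wants to investigate echogenicity and artefact problems "which may arise from age, body composition, mechanical valves, leads from implanted devices" and similar factors. Section 4.1 adds "The proportion of success and 95%CI will also be reported by patients characteristics", with age, BMI, gender and VT etiology as examples in an open list.

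The nearest safeguard is section 4.3: records are anonymised before they are shared with the company for its analysis.

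**The concern.** C and D are judgements by eye, and a positive view needs at least one of them. The protocol fixes the reader only as some member of the site team. As written, the reader may be the operator, may change from patient to patient, and may know the patient's build, age, valves and leads. The reader may also know how the software performed and how the other view was scored.

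Those patient factors are the ones whose effect on image quality the study is meant to investigate. A reader who expects poor images in a heavy patient, or in one with leads, may read a borderline image accordingly. The breakdown in section 4.1 could then partly reflect expectation. An operator who has just steered the probe also knows what the image ought to show, and may recognise a structure that the recording alone would not reveal.

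The scores also feed the secondary endpoint, because section 2.2 bases the virtual probe position on the view that scored best.

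**Working it through.** **1. Is the reader restricted anywhere?** The relevant sections, side by side:

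| Section | What it fixes | Does it mask or restrict the reader of C and D? |
|---|---|---|
| 2.2 | C and D read by a site team member | No |
| 3.1.1, 3.3 | History confirmed with the patient, in the procedure column | No |
| 3.1.2 | A trained investigator performs the procedure; images are watched live | No; the operator is not excluded from reading |
| 2.4 | Live display also shows metrics computed during acquisition | No; whether these underlie A or B is not stated |
| 4.3 | Anonymised records go to the company | No; C and D are read at the site |
| 7.3 | Study documents carry a participant number | No; reading from coded files is not required |

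The protocol permits an unmasked reader. It does not say that the reader will be the operator.

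**2. When does a visual call change a patient's result?** Take the parenthesis in the section 2.2 rule as its definition:

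- View positive = (A or B) and (C or D).
- Patient positive = at least one view positive.

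The visual half of a view fails only if C = 0 and D = 0. A lenient call therefore matters only where no view would otherwise pass and some view has a software point but neither visual point. In such a view, one extra point in C or D makes the patient positive. A strict reader would have to withhold both C and D in every view that would otherwise pass.

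**3. How strongly does the rule dampen a shift?** The protocol gives no pass rates, so this is an illustration under assumed, independent rates.

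- A or B 0.9, C 0.8, D 0.6: one view 0.9 × (1 − 0.2 × 0.4) = 0.828; better of two 1 − 0.172² = 97.0%.
- C raised to 0.9 and D to 0.7: one view 0.9 × (1 − 0.1 × 0.3) = 0.873; better of two 1 − 0.127² = 98.4%.

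Ten points of leniency in each visual item move the overall proportion by 1.4 points here. Correlation between items or views would weaken the damping.

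**4. The protocol's own precision figures.** Section 4.1 gives lower 95% limits of 73% at 22/24 and 79% at 23/24. The exact (Clopper-Pearson) lower limit is the 2.5% quantile of Beta(x, n − x + 1):

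- x = 22, n = 24: 73.0%
- x = 23, n = 24: 78.9%

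Both reproduce.

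**5. Scale of one patient-level call.** 1/24 = 4.2 points.

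| Successes | Proportion | Exact 95% CI |
|---|---|---|
| 22/24 | 91.7% | 73.0% to 99.0% |
| 21/24 | 87.5% | 67.6% to 97.3% |

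In a subgroup of 12 (assumed; the protocol gives no subgroup sizes), one call is 1/12 = 8.3 points. For example, 11/12 has an exact CI of 61.5% to 99.8%, and 10/12 has 51.6% to 97.9%. These figures show sensitivity to a single call and do not estimate bias.

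**The case against.** **The protocol is silent, and silence is not error.** Watching the images during acquisition is not scoring them. Section 2.4 provides stored session records, and no section says that C and D are scored live or by the operator. Reader assignment and masking often sit in an analysis plan or reading manual. The first part stands: a reader might infer that the operator scores during the session, and the text does not support that. The second part does not remove the point. Section 2.2 names the reader within the primary endpoint definition, and names that reader too loosely.

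**The endpoint rule leaves the reader little leverage.** This stands for the overall proportion. A reader might treat the visual reading as the sole decider and infer that modest leniency would greatly raise the chance of reaching 22/24. That would skip the rule. With both views available and the software half met, a patient fails visually only if, in both views, no listed structure is identifiable and the heart also disappears with respiration. The protocol gives no support for that being common, least of all while the software still passes on the same images.

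**22/24 is not a pass mark, and the breakdown is not a test.** Both stand. Section 4.1 uses 22/24 as an aim for precision. It reports subgroup proportions with intervals and states no comparison. Valves and leads come from section 2.1 and are not among the examples in 4.1, although that list is open.

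**Masking does not cure leniency.** This stands too. Masking limits readings that differ by patient type. A single reader who is generous to everyone remains generous.

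**Conclusion.** The point holds as a risk of bias that the protocol permits, not as a demonstrated bias. C and D are subjective, one of them is needed for every positive view, and the protocol neither excludes the operator nor masks the reader to patient characteristics, A and B, or the other view.

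The more exposed result is the breakdown by characteristics, because the reader may know the very factors under study and subgroups of a 24-patient sample are small. The overall proportion is better protected by the structure of the rule. The size of either effect cannot be computed, since the protocol gives neither reading error nor pass rates; the 4.2 points per patient and the limits of 73.0% and 67.6% serve only as a scale.

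The plan should be changed, because the remedy is cheap and the materials for it already exist. The point does not invalidate the study.

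**What to change.** Add one paragraph to section 2.2:

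- C and D are scored from the stored, coded recordings after acquisition is complete, not during the session.
- One existing site team member scores all patients, preferably one who did not operate the probe.
- Apical and parasternal recordings of all patients are mixed in random order.
- The reader has no access to the CRF or to the patient's other view.
- C and D are locked before A and B are returned.

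Sections 2.4 and 7.2 already provide for saved session records, and 7.3 for participant numbers. The cost is the paragraph and a random reading list, with no extra patient, procedure or reader.

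There are three small downsides. Reading waits until acquisitions are finished. Leads or valves visible in the image cannot be masked. Uniform leniency of the single reader is not removed.

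### Criterion D of the primary endpoint gives its point by default to a view in which the heart is never visible, so such a view can meet the visual half with C = 0

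*Protocol*

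**What the plan says.** Protocol section 2.2 scores each imaging view (apical and parasternal) on four binary items. A and B come from the software, C and D from visual inspection by a member of the clinical team.

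- C is 1 if at least one of three listed cardiac structures can be identified, and 0 otherwise. No duration is required.
- D is 0 if the reader "identifies that the heart becomes invisible for part of the time due to tissue motion linked to respiration", and 1 otherwise.
- The view is judged by this rule: "If the score is 2 (at least 1 point in A or B and 1 point in C or D) or higher". One positive view of the two makes the patient a success.

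The same section states what the endpoint is meant to capture: "positive evaluation in image interpretation metric and positive visual inspection of the ultrasound images". Section 2.1 adds the wider purpose: "to investigate potential echogenicity and artefact issues, which may arise from age, body composition, mechanical valves, leads from implanted devices". Section 3.1 says: "Patients with cardiac or non-cardiac implants in the thorax area are of interest for the research".

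**The concern.** D scores 0 only if two things hold together: the heart is lost for part of the time, and breathing is the cause. Everything else earns the point. The item never asks whether the heart was seen at all, so a view with no visible heart scores D = 1. C is necessarily 0 in such a view, yet the D point alone satisfies the visual half.

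With C = 0, a heart that is visible but fades at times with respiration fails the visual half, while a heart that is never visible passes it. That is the reverse of any sensible ranking of image quality, in a study whose primary purpose is to judge image quality. At stake is the primary success proportion, which could include patients whose only positive view shows no heart.

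**Working it through.** **Inputs.** The definitions of A to D and the view rule come from section 2.2. The sample size of 24, the aim of 22/24 and the stated lower 95% limit of 73% come from section 4.1.

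**Step 1: the plan's own figure.** The exact (Clopper-Pearson) lower limit for x successes in n is the 2.5% quantile of a Beta(x, n − x + 1) distribution. For 22/24 this is Beta(22, 3), which gives 73.0%. The stated 73% is reproduced, and the scoring gap does not affect that calculation.

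**Step 2: the rule applied to each image state.** A view is positive if (A or B) and (C or D). The corrected D is 1 only if the heart is visible in the view and is not lost in part through respiration.

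| Image state | C | D as written | Visual half as written | D corrected | Visual half corrected |
|---|---|---|---|---|---|
| Never visible | 0 | 1 | met | 0 | not met |
| Lost in part, respiratory | 0 | 0 | not met | 0 | not met |
| Lost in part, respiratory | 1 | 0 | met | 0 | met |
| Lost in part, other cause | 0 | 1 | met | 1 | met |
| Lost in part, other cause | 1 | 1 | met | 1 | met |
| Steadily visible | 0 | 1 | met | 1 | met |
| Steadily visible | 1 | 1 | met | 1 | met |

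The visual half is met in 6 of 7 states as written and in 5 of 7 with D corrected. Only the never-visible state changes. A or B is met in 3 of the 4 combinations of A and B, so over all 7 × 4 = 28 combinations the positives go from 6 × 3 = 18 to 5 × 3 = 15. These are counts of logical states, not frequencies. The corrected D is never higher than D as written, so the correction can only lower the success proportion or leave it unchanged.

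**Step 3: does the result depend on how the view rule is read?** The text in brackets is taken as the rule. If only the total of 2 were used, a never-visible view (C = 0, D = 1) would still be positive with one software point, since 1 + 1 = 2. A view with C = 0 and D = 0 would need both A and B. The reversal remains.

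**Step 4: does other text close the gap?**

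- Section 4.2 removes only patients who lack ultrasound imaging data. A recording without a visible heart is still data.
- Section 3.1.2 (Cardiac Motion monitoring) says, for the apical view: "During data acquisition, the image quality of the ultrasound images is visually monitored". This may make such views rarer, but it sets no scoring rule.
- Criterion B asks for "a motion amplitude lower than 30 mm and if the number of breathing cycles matches the one observed" from chest motion. Its wording does not require the heart to be seen, so the software half does not exclude such a view on paper.

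**Step 5: size, as an illustration.** Let k be the number of patients positive only by this route. The documents do not give k; it is an assumption. Starting from a reported 22/24:

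| k | Without these patients | Exact lower 95% limit |
|---|---|---|
| 0 | 22/24 = 91.7% | 73.0% |
| 1 | 21/24 = 87.5% | 67.6% |
| 2 | 20/24 = 83.3% | 62.6% |

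Each such patient is worth 1/24 = 4.2 points.

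**The case against.** The strongest reply is that several unlikely things must coincide. The view must show no heart although a trained investigator positioned the probe for cardiac viewing with live images on screen. The software must still return a cardiac phase error below 0.1, or a breathing analysis that meets both parts of B. The patient's other view must also fail. The protocol does not show that a view without a heart would pass A or B. This stands, and it is why no effect size is claimed. It does not repair the rule, which a reader could apply sensibly only by departing from its wording.

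It can also be said that C is the item for poor echogenicity and artefact and D the item for respiratory loss, so D need not penalise the former. As a division of labour this is legitimate, and it limits the point. A reader might infer that every non-respiratory loss of the heart is wrongly rewarded. The documents do not support that. C has no duration requirement, so a heart seen for part of the recording will usually give C = 1 and the view passes whatever D is. Whether D should also count such losses is a design choice.

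A reader might further infer that the default point distorts the secondary endpoint, because the virtual probe position is "based on the best probe view as assessed by scoring for the primary endpoint". The protocol does not say that the best view is the one with the highest total score, so this does not follow.

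**Conclusion.** The point holds for the never-visible heart. As written, D gives that view the visual point, ranks it above a view with C = 0 that fades with breathing, and so contradicts the stated aim of a positive visual inspection. This conclusion rests only on the literal wording of section 2.2 and on the absence of any other text that closes the gap.

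The bias has one direction: it can only raise the success proportion. Its size cannot be estimated from the protocol and may be zero. The 4.2 points per patient are arithmetic, not a forecast, and nothing in the documents shows that any patient would be affected. A reader might also infer that the feasibility conclusion could be overturned; the documents do not support that, since 22/24 is an aim with no decision rule attached. A steadily visible heart in which no listed structure is identified (C = 0, D = 1) is scored as the protocol intends and is not at issue.

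**What to change.** In section 2.2, turn D into a positive condition: score 1 only if the heart is visible in the view and is not lost for part of the time through respiratory tissue motion; score 0 otherwise, expressly including a heart that is not visible at all. Record any non-respiratory loss and its reason descriptively, which also serves the aim in section 2.1.

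The C-or-D rule and the respiratory purpose of D stay as they are. Scoring D = 0 for partial loss from any cause would go further: it would make D a general continuity item and count brief dropouts when the parasternal probe is held by hand. Making C = 1 compulsory would also go further. Either would be a sponsor decision and is not part of this correction.

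The cost is one sentence and one descriptive entry, from the same readings, and a success proportion that may be slightly less favourable.
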